Despite the above, the detection of *viable* virus in aerosols generated by humans has not been shown before (as far as we know). The generation of information about the presence of viable influenza virus in the environment will be fundamental to our understanding of the routes of transmission. With this in mind, we have recently attempted to demonstrate that viable influenza virus can be found in aerosols as part of the Proof of Concept study (ITSDG-01) mentioned earlier. In preparation for this, the University of Nottingham received sampling equipment from CDC/NIOSH (identical to that used by [name] et al above). Prior to its use we approached the Health and Safety Laboratory in England to pilot setting-up of the sampling equipment, calibration and evaluating the utility of the sampler for capturing live influenza. Following experiments that involved aerosolizing influenza virus in a laboratory, live virus could be detected by an air sampler using the virus plaque assay technique (and PCR results were concordant). Following on from this, air sampling recently took place during the proof of concept study – results are awaited. Thus the technique of air sampling using the CDC/NIOSH equipment has been validated in the UK at the Health and Safety Laboratory and (pending results) during a quarantine based challenge study.

Research at CEH has already demonstrated in preliminary research the capacity of the influenza virus to persist in sewage influent for over 2 hours with only a 60% loss in total counts (quantitative PCR). Given that our ability to detect the virus spans >8 orders of magnitude using quantitative PCR, a 60% decline is negligible (e.g., lowering virus counts from 5.0 x 10^6 to 2.0 x 10^6). Hence, there is every reason to expect that if the virus is being shed by influenza-infected patients, the virus should be recoverable in the sewage influent.

6. Research Objectives

The objectives of the proposed study are:

Primary:

- To determine the quantity of infectious virus present in the nose, on surfaces, in air and in stools, according to time from symptom onset, symptom constellation (e.g. presence of cough or sneeze), distance from source and particle size (in air);
- ii) To correlate serial virus shedding in pandemic influenza patients against data on near-patient environmental contamination (surfaces and air).

Secondary:

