- iii) To describe virus shedding (quantity of infectious virus) and duration according to important patient sub-groups, notably adults and children, those with mild illness (community patients) and those with more severe disease (hospitalised patients)
- To determine if aerosol generating procedures (most likely to be performed on ITU) are associated with changes in the quantity of environmental contamination with live virus, either in relation to quantity or particle size, or distance from source.
- v) To investigate the possibility of estimating the number of influenza-infected individuals in an area by the quantity o influenza virus recovered in sewage influent.

Policy related (to provide scientific data suitable for policy refinement on):

- vi) 'Safety distances' around patients with pandemic and seasonal influenza
- vii) Appropriate use of respiratory personal protective equipment (RPPE) and infection control practices for pandemic and seasonal influenza, according to patient type, illness severity and time since symptom onset
- viii) Antiviral treatment duration for patients with pandemic influenza
- ix) To develop an alternative surveillance strategy for quantifying influenza infections in a community.

The primary objective of this study is to correlate the amount of virus detected in a patient's nose with that found in the environment around them and with the time since illness onset and symptom severity. The point being that so called 'virus shedding' studies that measure virus recovered from the nose do not actually define environmental contamination and hazard to others. To the best of our knowledge such work has not been done before. The study has the potential to address the issues of how, when and where in relation to virus transmission, all of which we believe could inform policy. By collecting stools, we can also correlate influenza shedding in the nose with the stool and thereby provide a mechanism for generating estimates of influenza in the stool to populate the sewage-based epidemiology model.

How – Are touched surfaces important in virus transmission and does respired air present a significant transmission route?

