- Hospitalised adults: 4 patients, 4 sampling days (sampling every other day for 8 days), 6 samples each time (3 from each sampler) = 96
- Hospitalised children: 4 patients, 6 sampling days (sampling every other day for 12 days), 6 samples each time (3 from each sampler) = 144
- Adults in their own homes: 4 patients, 4 sampling days (sampling every other day for 8 days), 6 samples each time (3 from each sampler) = 96
- Children in their own homes: 4 patients, 6 sampling days (sampling every other day for 12 days), 6 samples each time (3 from each sampler) = 144

A sample patient schedule can be seen at appendix 2.

4. Stool Sample Collection

Detailed instructions will be provided explaining how to obtain a sample. We will ask the patient to empty their bladder first if possible. They will then place a collecting plate in the toilet bowl which will catch the stool. A sample can then be taken and put in the container. The remaining stool is then tipped into the toilet and flushed away. The plate is disposed of in a rubbish bag. Once the sample container has been securely capped, it should be placed in a specimen bag and kept in a small cooler box (which will be provided). Hand washing / hygiene measures will be stressed. Stool samples will be collected daily along with the other samples.

Sample Processing (stool samples dealt with separately – see below)

The generation of \approx 3,300 samples for both PCR and PA is a considerable amount of work requiring not just expertise but also significant laboratory resources, including time. Thus, it is not possible to generate results on all samples collected in a short period. We therefore propose to define a sample processing protocol based on results from the first few cases. It could include the following;

- If a patient tests negative for swine flu (as part of NHS care) we will exclude them from further study.
- Environmental swabs will not be processed if nasal swabs from a case are PCR negative.
- Environmental swabs will only be processed if nasal swabs from a case show a high viral load.
- Environmental swabs will not be processed for PA if nasal swabs from a case are PA negative.

Note; samples that are not processed rapidly will be retained for analysis in the future should this be of interest.

Transport and storage of participant samples

Transport

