Collected samples will be placed into viral transport medium and kept on 'wet' ice until being frozen at -80^oC. For hospital samples freezing would likely happen within 4 hours and community samples within 9 hours. Samples will be carried / transported locally by researchers in dedicated equipment. Samples will be sent to the Cambridge laboratory once each week from each of the 3 centres and will be transported by a professional delivery company.

Storage

Samples will be kept frozen until analysis at the HPA microbiology laboratories, Addenbrookes Hospital, Cambridge. They will be identifiable through participant study codes, participant initials and date of birth. Following analysis all samples will be destroyed. Analysis is expected to be complete by February 2010

Laboratory analyses

Sample Processing

The generation of \approx 3,300 samples for both PCR and PA is a considerable amount of work requiring not just expertise but also significant laboratory resources, including time. Thus, it is not possible to generate results on all samples collected in a short period. We therefore propose to define a sample processing protocol based on results from the first few cases. It could include the following;

- If a patient tests negative for swine flu (as part of NHS care) we will exclude them from further study.
- Environmental swabs will not be processed if nasal swabs from a case are PCR negative.
- Environmental swabs will only be processed if nasal swabs from a case show a high viral load.
- Environmental swabs will not be processed for PA if nasal swabs from a case are PA negative.

Note; samples that are not processed rapidly will be retained for analysis in the future should this be of interest (note this will happen within the study timecourse).

Laboratory Testing

- HPA Laboratory, Addenbrookes Hospital, Cambridge will be process samples by PCR methods. The contact person is [name].
- University of Cambridge department of pathology, virology laboratory, Addenbrookes Hospital, Cambridge will process samples for virus culture. The contact person is [name].

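### If adopted as final, the candidate rules that test environmental swabs only when the nasal result is positive or high would weaken the primary nose-to-environment correlation

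*Protocol*

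**What the plan says.** Section 6 of the protocol sets as primary objective (ii) "To correlate serial virus shedding in pandemic influenza patients against data on near-patient environmental contamination". It explains that studies relying on nasal recovery "do not actually define environmental contamination and hazard to others". Section 11 (Proposed Sample Size) says that most analyses will be correlations of this kind. It claims power above 80% for correlations of 0.55 at n=25, 0.4 at n=50 and 0.3 at n=100.

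Section 10 gives the same list of possible processing rules twice, under Sample Processing and again under Laboratory analyses. It is introduced by "We therefore propose to define a sample processing protocol based on results from the first few cases. It could include the following". Three items concern environmental swabs. The first would leave them untested where the patient's nasal result is negative by PCR. The second sets a stricter condition: "Environmental swabs will only be processed if nasal swabs from a case show a high viral load". The third would withhold the plaque assay from them where the nasal plaque assay found nothing.

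No threshold is given for a high load. A note after each list says that samples not tested quickly will be kept for later analysis if that is thought worthwhile. The second version adds that this will take place before the study ends.

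**The concern.** The study exists because nasal load is not assumed to stand in for environmental contamination. A rule that measures the environment only where nasal load is positive or high builds that assumption into the data. Three things would follow if the rules became final and the kept swabs stayed untested:

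- The nasal range would be cut off from below. The correlation would be smaller than the one the study was sized to detect, and would rest on fewer pairs.
- The descriptive environmental means planned in Section 11 would come from the heavier shedders only.
- For the swabs covered, a low or negative nose with a contaminated surface could not be seen. That combination bears on how long precautions are needed, which Section 6 wants to inform.

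Entry already requires a positive influenza test. Section 8 concedes that the near-patient test may favour patients with higher viral load, so this would be a second selection in the same direction.

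**Working it through.** **Inputs.** Correlations and group sizes are from Section 11. Two-sided alpha of 0.05 is assumed, because the protocol states no alpha and mentions a two-tailed test only for the duration comparison. The share of patients whose load counts as high is not given, so 75%, 50% and 25% are tried. Each patient is treated as one nose–environment pair, bivariate normal on the log scale.

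**Step 1: the plan's own figure.** Power = Φ(atanh(r)·√(n−3) − 1.96).

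- r=0.55, n=25: 82.7%
- r=0.40, n=50: 82.8%
- r=0.30, n=100: 86.2%

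The stated power above 80% is reproduced.

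**Step 2: effect of keeping only the upper part of the nasal range.** With cut-point c and kept share k, let λ = φ(c)/k. The variance ratio is u² = 1 + cλ − λ², and the restricted correlation is r′ = r·u/√(1 − r² + r²u²). The variance ratio is 0.535, 0.363 and 0.242 for 75%, 50% and 25% kept.

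Worked case, r=0.55 with half kept: c=0, λ=0.798, u²=0.363, u=0.603. Then r′ = 0.55×0.603/√(0.6975 + 0.3025×0.363) = 0.369. With n=12, power is 21%.

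| True r (full n) | Top 75%: r′, n, power | Top 50%: r′, n, power | Top 25%: r′, n, power |
|---|---|---|---|
| 0.55 (25) | 0.43, 19, 46% | 0.37, 12, 21% | 0.31, 6, 8% |
| 0.40 (50) | 0.30, 38, 46% | 0.25, 25, 23% | 0.21, 12, 9% |
| 0.30 (100) | 0.22, 75, 49% | 0.19, 50, 25% | 0.15, 25, 11% |

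Simulation with 20,000 studies per cell gives 47–50%, 22–26% and 9–11%, within about 3 points of the formula.

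**Step 3: separating selection from smaller numbers.** A random half leaves r unattenuated and gives power of 46% (n=12), 51% (n=25) and 56% (n=50). For r=0.55, power falls by about 37 points (82.7 to 45.8) from testing half as many and by a further 25 (45.8 to 21.2) from choosing the upper half. Conversely, if n were unchanged, attenuation from keeping the top half alone would leave power of 43–46%.

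**Step 4: means and slope.** With the top half kept, the mean environmental load shifts by r×0.798: +0.44, +0.32 and +0.24 SD for r of 0.55, 0.40 and 0.30. The regression slope is essentially unchanged: 0.545, 0.394 and 0.303 in simulation.

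**The case against.** The case against is substantial, and much of it stands.

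- **Nothing is fixed.** The list is of things the processing protocol might contain, prompted by limited laboratory capacity in the short term. A reader might infer that the correlation is already weakened by design; the text does not say so.
- **Samples are kept.** If all the kept swabs were tested, neither the truncation nor the gap would remain. A reader might infer that the study could never show contamination outlasting nasal clearance, which is too strong. What remains is that later testing depends on interest. The added remark about timing does not clearly commit to it, and Section 10 also provides for destroying samples after analysis.
- **Patient or day.** The wording about nasal swabs from a case may be a patient-level rule. On that reading a patient who qualifies has all environmental swabs tested, including those from days after the nose clears, and the PCR-negative rule mainly removes people never confirmed to have influenza. The protocol does not say which is meant.
- **Air.** The rules name swabs. Air particles are collected in tubes or on filter paper, so a loss of air data cannot be inferred.
- **Untested swabs counted as negative.** This would create a spurious correlation, but nothing in the protocol proposes it.
- **Bias of the model.** Selection on the explanatory variable does not bias the slope of a correct linear model, so the third-stage regression in Section 11 would mainly lose precision and range. A slope fitted only at high loads would still have to be extrapolated to low and negative ones.

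**Conclusion.** The concern holds conditionally. If the candidate rules were made final and the kept swabs were not all tested, the protocol's primary correlation would be attenuated. Its power would fall below the stated level for every assumed share: about 46–49%, 21–25% and 8–11% for 75%, 50% and 25% kept. Environmental means would be biased upward, by 0.24 to 0.44 SD with half kept. Low-nose, positive-surface combinations would be missing for the swabs covered.

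The figures rest on one uncensored normal pair per patient, an assumed alpha and an assumed share kept. The planned data are serial and will include results at an assay floor, so the numbers show scale and are not predictions. They also reflect selection between patients; whether the rules act per patient or per day is unclear, as is whether they reach air samples. It would be wrong to attribute the whole loss of power to selection: part comes simply from testing fewer swabs. Section 11 allows for neither effect.

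**What to change.** In both places in Section 10 where the list appears:

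- For patients with confirmed influenza, use nasal results only to set the order in which environmental swabs are tested, and commit to testing the kept swabs before the correlation analysis.
- If capacity rules that out, test a pre-specified random subset, or one stratified by nasal load with known sampling fractions. It should include low and negative nasal days and follow the same rule for PCR and plaque assay. Use the sampling fractions when estimating the correlation and the environmental means.
- State whether any rule acts per patient or per day, and whether it covers air samples.
- Screening out patients never confirmed to have influenza can stay.

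Taking only the two extremes of nasal load is not a safe shortcut if the unweighted correlation is reported. At half the swabs it raises power to about 76–83% under the normal model, but inflates r to 0.67, 0.51 and 0.39 against true values of 0.55, 0.40 and 0.30.

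The change is one of wording. Testing every kept swab uses laboratory time that the candidate rules would have saved; a subset can be held to the same number of assays. In either case more assays will come back negative. With a subset, the power in Section 11 must be restated; for a random half it is about 46–56%.

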11. STATISTICS

Proposed Sample Size

We will aim to recruit groups of about 25 patients with recent onset H1N1 influenza in each of the four main sub-groups identified under 'research methods'. Most statistical analysis will involve examining correlations between virus shedding and virus deposition in the environment. The figure below illustrates that sub-group sizes of 25, which also allow pooling of data by adults or children (50 per group) or the whole population gives high statistical power (>80%) to detect correlations of >0.55 in groups of size n=25, 0.4 in groups of size n=50, and 0.3 in groups of size n=100.

As regards the duration of virus shedding, these data will be primarily descriptive but it will be important to be able to make formal statistical comparisons of the duration of shedding between adults and children. However by pooling data into adults vs. children (n=50 per group) differences of 5 days (adults) vs. 6 days (children) (two tailed-test) could be detected with >80% provided that the coefficient of variation in shedding was 0.3 or less. For larger differences e.g. 5 days vs.7 days or 5 days vs. 8 days, the study is well powered to coefficients of variation up to 0.6.

Statistical Analysis

Virus Shedding Study Protocol Version 1.2, 27AUG2010

Page 28 of 38

We will perform a detailed descriptive analysis of the data. The symptom constellation of patients in the different groups will be presented. The mean (standard deviation, range) of the quantity of infectious virus in the patient, on surfaces and in the air will be plotted for each patient group and as a function of time since onset, symptom constellation and distance from source (when relevant). The mean (standard deviation, range) duration of shedding will also be plotted for each patient group and as a function of symptom constellation. For a better representation of inter-individual variation (which is expected to be important), we will also plot individual trajectories.

In a second stage, formal tests will be used to determine which outcomes are significantly associated / correlated. Statistical tests will also be implemented to compare the mean duration of shedding among children and adults as well as among mild and severe cases.

In a third stage, a Generalized Linear Model with random effects will be used to determine the key predictors for the quantity of infectious virus in surfaces and in the air. A survival analysis will also be implemented to assess the key predictors for the duration of viral shedding.

Outcome Measures

- 1. Virus shedding and deposition as measured by virus culture and quantitative PCR. (Quantitative PCR and plaque assay of respiratory virus specimens (nasal swabs) from patients and surfaces and air around them). Virus shedding and deposition as measured by virus culture and quantitative PCR.
- 2. Daily symptom scores and patient temperature readings
- 3. Medication logs
- 4. Household/ward daily temperature and humidity logs

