- 4. In order to ensure that patients with relatively recent onset of symptoms are recruited we will set exclusion criteria of >48h after symptom onset for community cases (but aim for recruitment of cases who are within 24h of symptom onset); and > 96h after symptom onset for hospitalised cases (but aim for recruitment within 48h).

Study Management

The study will be managed from a central coordinating site (Nottingham University) by a project manager and administrator. Data will be collected on to source documents and CRFs by the clinical team. Data will subsequently be entered onto a database. All data will be stored at the

University of Nottingham and they will act as custodian of it. Data generated from CEH will be shared with the project team and stored along with the rest of the virus shedding data.

Duration of the study and participant involvement

Each participant's involvement with the study will last for up to 2 weeks. No further follow up of participants is planned. Enrolment will begin in August 2009 and will cease in October 2009. Processing of samples collected and data extraction will continue until February 2010

End of the Study

The end of the trial will follow the completion of the laboratory analysis of samples and subsequent data analysis and presentation.

9. Selection and withdrawal of participants

See Appendix 1 for study outline

Cases

We propose the study of small numbers of symptomatic pandemic influenza patients from four groups:

- i) Hospitalised adults
- ii) Hospitalised children (up to the age of 16 years)
- iii) Adults in their own homes
- iv) Children in their own homes (up to the age of 16 years)

We regard these four groups as the minimum desirable based on known differences in virus shedding and respiratory etiquette between adults and children and likely differences in symptom severity between patients managed in the community and those who require hospital admission.

Hospital cases once discharged will be followed up and further sampling will take place in the patient's own home with consent. Similarly if a community patient is admitted to hospital mid-way through sampling we would attempt to follow them up in hospital.

Recruitment

HOSPITAL CASES:

Hospital cases will be identified through the clinical teams looking after patients in the participating centres.. We will not receive personal information about patients or approach them until their consent for us to do so has been granted.

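### The pooled shedding-versus-environment correlations (n=50, n=100) are powered as unadjusted correlations across groups that the protocol expects to differ, so they can mix group differences with the patient-level link.

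*Protocol*

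**What the plan says.** Section 6 (Research Objectives) puts the main question at patient level: "The primary objective of this study is to correlate the amount of virus detected in a patient's nose with that found in the environment around" that patient. Section 11 (Proposed Sample Size), repeated in the synopsis, adds that "Most statistical analysis will involve examining correlations between virus shedding and virus deposition in the environment". On pooling it reads: "sub-group sizes of 25, which also allow pooling of data by adults or children (50 per group) or the whole population gives high statistical power". The size of that power is given as ">80%) to detect correlations of >0.55 in groups of size n=25, 0.4 in groups of size n=50, and 0.3 in groups of size n=100". Under Statistical Analysis, the second stage says that "formal tests will be used to determine which outcomes are significantly associated / correlated", with no mention of recruitment group. The third stage is a generalised linear model with random effects for virus on surfaces and in air; its predictors are not listed.

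Section 9 (Cases) explains that the four groups (hospital or home, adult or child) are "based on known differences in virus shedding and respiratory etiquette between adults and children and likely differences in symptom severity" between home and hospital patients. Under Recruitment it expects hospital patients probably to have a higher viral load and slower decline, but also says that some may be past their peak. Section 10 lists different surfaces for hospital and home, and expects three surface samples per visit in hospital against six at home.

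**The concern.** A correlation computed across a mixture of groups has two sources: the association among patients of the same kind, and the association between the group means. If one group is higher on both variables, the pooled correlation is positive even when a patient's nasal load tells nothing about that patient's surroundings. If a group is higher on one variable and lower on the other, a real link is diluted.

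Section 6 wants to know whether nasal virus measures the hazard around the patient, and the answer is meant to steer policy between hand hygiene and respiratory protection. A significant pooled correlation that shows only that children differ from adults, or wards from homes, would answer a different question. Pooling matters because the single-group correlations are powered only for values of about 0.55, so evidence on a moderate correlation has to come from the pooled samples.

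**Working it through.** **Inputs.** From section 11: r = 0.55, 0.4 and 0.3 at n = 25, 50 and 100. From section 10: surface data expected from 12.5 + 12.5 hospital and 25 + 25 home patients, 75 in all, and air data from 16 patients, four per group. Assumed: two-sided 5% level (section 11 gives no level, and says "two tailed-test) could be detected with >80"% only for the comparison of durations); one pair of values per patient; normal data; group shifts of 0.25 to 1.0 within-group SD, since the documents give none for virus quantity or deposition.

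**The plan's own figures.** Power ≈ Φ(atanh(r)·√(n−3) − 1.96):
- n=25, r=0.55: 0.6184 × 4.690 − 1.96 = 0.940, power 82.7%
- n=50, r=0.4: 0.4236 × 6.856 − 1.96 = 0.944, power 82.8%
- n=100, r=0.3: 0.3095 × 9.849 − 1.96 = 1.088, power 86.2%

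All exceed 80% as stated, and all are for a simple correlation with no adjustment.

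**Effect of a group shift.** Let half the patients be shifted by d SD in the same direction on both variables, with within-group correlation ρ. The pooled correlation is (ρ + d²/4)/(1 + d²/4). With ρ = 0 and d = 0.6 this is 0.09/1.09 = 0.083. At n=100, atanh(0.083) × 9.849 ≈ 0.815, and the rejection rate is Φ(0.815 − 1.96) + Φ(−0.815 − 1.96) ≈ 13%. Simulation agrees:

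| Child-adult shift on both variables, ρ = 0 | Pooled r | Rejects, n=100 | Rejects, n=75 (surface data) |
|---|---|---|---|
| 0.25 SD | 0.015 | 5% | 5% |
| 0.5 SD | 0.059 | 9% | 8% |
| 0.6 SD | 0.083 | 13% | 10 to 11% |
| 0.75 SD | 0.123 | 23% | 18 to 19% |
| 1.0 SD | 0.200 | 52 to 53% | 41 to 42% |

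In the n=50 pools by age, only a hospital-home shift matters. There the rejection rate is about 7% at 0.5 SD and 29% at 1.0 SD.

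**Other direction.** With ρ = 0.3 and opposite shifts of 0.6 SD, the pooled correlation is (0.3 − 0.09)/1.09 = 0.193, and power at n=100 falls from about 86% to 48%. With same-direction shifts it is 0.39/1.09 = 0.358, and power rises.

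**Adjusting for group.** A partial correlation given the four groups costs three degrees of freedom at n=100 or n=75, and one at n=50 (two groups). Replace n−3 by n−6 or n−4:
- n=100, r=0.3: 0.3095 × √94 − 1.96 = 1.041, power 85% (unadjusted 86%)
- n=50, r=0.4: 0.4236 × √46 − 1.96 = 0.913, power 82% (82 to 83% by simulation; unadjusted 83%)
- n=75, r=0.3: 0.3095 × √69 − 1.96 = 0.611, power 73% (73 to 74% by simulation; unadjusted 75%)

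In simulation this test rejects about 5% of the time under ρ = 0 at every shift tried.

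**The case against.** The strongest reply is that the protocol does not commit to the criticised test. The sample-size paragraph says that the group sizes permit pooling. The analysis text names no particular correlation, and the choice between a simple and a partial correlation is normally left to the analysis plan. This stands in part: a reader might infer that an unadjusted pooled correlation is fixed as the primary test, and the text does not say so. But the protocol does name the pooled samples and attach power to them, and that power is for an unadjusted correlation.

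Second, other planned analyses help. The n=25 correlations are free of the problem, the descriptive plots by group would show any shift, and the third-stage model could include group. All true. However, the n=25 analyses reach only large correlations, and the model names no predictors and carries no stated power.

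Third, between-group variation may be signal. The objective on correlation does not restrict itself to patients of one kind, and section 5 treats symptom severity as a proxy for viral load, so adjusting for hospital or home may remove part of what is being studied. This is a fair reason to report both correlations, but not to leave them undistinguished.

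Fourth, the size is assumed. The documents give no shift in virus quantity. That deposition differs is inferred from etiquette and from the surfaces sampled. A 0.6 SD difference can be derived from the duration calculation (5 against 6 days at a coefficient of variation of 0.3: 1/√((1.5² + 1.8²)/2) = 0.60), but that is a detectable difference in duration, not an expected one in quantity. This stands.

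**Conclusion.** The point holds as a weakness in how the pooled correlations are set up. The protocol justifies n=50 and n=100 on an unadjusted basis while giving reasons to expect the pooled groups to differ. The consequence ranges from negligible at 0.25 SD, through 9% false rejection at 0.5 SD, to about half of trials at 1.0 SD (n=100), and is somewhat smaller at the 75 patients expected to have surface data. These figures rest on the assumed shifts, normal data, one pair per patient and a two-sided 5% level.

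Two stronger readings are not supported. A reader might infer that the stated powers are wrong, or hold only when group means are equal. They are correct for a pooled correlation of the stated size, and same-direction shifts raise the chance of rejection. A reader might also infer that pooling will hide a real link. That needs opposite shifts in shedding and deposition, which the protocol nowhere predicts.

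**What to change.** In section 11 and the synopsis, state that any formal correlation pooled across recruitment groups is a partial (within-group) correlation adjusted for those groups. Averaging group-specific Fisher-z values is not a good substitute: with four air-sampled patients per group, each has weight n−3 = 1.

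Quote the pooled power on the adjusted basis: about 85% for r=0.3 at n=100, 82 to 83% for r=0.4 at n=50, and about 74% for r=0.3 at the 75 patients expected to give surface samples. Report the unadjusted pooled correlation next to it, labelled as including between-group differences.

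The change is wording only, with no new data. If the groups have equal means, it costs about 1 to 2 points of power.
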